5.1.3.3 Safety Analysis

Adverse events and their most severe reaction levels will be summarized according to the criteria of the 5th edition of the NCI CTCAE. Additionally, adverse events will be summarized based on their severity and relationship with the investigational drug.

Descriptive summaries of laboratory test values primarily focus on abnormal values.

Laboratory test abnormalities will also be summarized according to the most severe level specified in the 5th edition of the NCI CTCAE.

6. Adverse Events

6.1 Precautions/Warnings

Treatment must be administered under the supervision and guidance of a specialized oncologist with experience in the use of relevant medications. Appropriate management of complications is only possible when adequate diagnostic and therapeutic equipment is readily available. Common adverse events include cutaneous reactions of the hands and feet, fatigue, rash, fever, stomatitis, diarrhea, anorexia, hoarseness, arthromuscular pain, abnormal liver function, leukopenia, and thrombocytopenia.

6.2 Detection of Adverse Events

Close monitoring of adverse events occurring in subjects must be conducted. This monitoring includes clinical laboratory tests. The evaluation should be based on the severity, seriousness, and relationship to the investigational drug of the adverse event.

The investigator is responsible for evaluating the relationship between all adverse events and the investigational drug. However, the principal investigator may delegate this judgment to other investigators participating in the study, while remaining accountable for the outcome. The investigator must provide a list of qualified personnel who have been authorized to perform this task.

6.3 Definition of Adverse Events

6.3.1 Adverse Events

Adverse events refer to any adverse medical events occurring in patients or subjects receiving investigational drug therapy. Adverse events do not necessarily have a causal relationship with the treatment. Therefore, adverse events may include any adverse and nonspecific signs (including abnormal laboratory test results), symptoms, or diseases temporarily associated with the investigational drug, regardless of whether the event is considered drug-related.

Adverse events occurring in humans (whether or not drug-related) include the following:

- adverse events that occur during the use of a drug by a professional;
- adverse events caused by drug overdose (whether intentional or accidental);
- adverse events caused by drug abuse;
- adverse events caused by discontinuation of medication;
- Adverse events that may be purely study-related (e.g., those caused by discontinuation of antihypertensive drugs during the washout period or serious adverse events) must be reported as adverse events, even if they are unrelated to the study medication.

Clinical pharmacological effects that do not occur or do not meet the expected outcomes, and are already recorded in the corresponding section of the CRF, shall not be recorded as adverse events. However, if they meet the criteria for a 'serious' adverse event, they must also be recorded and reported as serious adverse events. In this study, the progression or deterioration of existing tumors that meet the 'serious' criteria must also be reported as serious adverse events (SAEs). Investigators should also report symptoms and

signs arising from the progression or deterioration of existing cancers.

6.3.2 Serious Adverse Events

A serious adverse event refers to any adverse medical event occurring under any medication condition that meets one of the following criteria:

- leading to death;
- threat to life ;
- resulting in hospitalization or longer hospital stays for patients;
- resulting in permanent or significant loss of the ability to work or disability;
- congenital malformation or congenital defect;
- Major medical events.

Life-threatening: The term 'life-threatening' is defined as 'severe', indicating that the subject is at risk of death when the adverse event occurs. It does not refer to adverse events that may lead to death under more severe hypothetical conditions.

Hospitalization: Any adverse event that results in a patient being hospitalized or that prolongs the length of hospitalization is considered serious, unless one of the following exceptions applies:

- Stay in hospital for no more than 12 hours;
- perhaps
- Admission was pre-planned (i.e. pre-scheduled surgery or elective surgery prior to the start of the study);
- perhaps
- Hospitalization was not associated with adverse events (e.g. hospitalization for convalescence purposes).
- Note: Any invasive treatment performed during hospitalization may meet the criteria for a 'major medical event' and may therefore require reporting as a serious adverse event based on clinical judgment. Furthermore, if local regulatory authorities require a more stringent definition, the local regulations shall prevail.

Disability: means that a person has a severely impaired ability to perform daily activities.

Major Medical Event: Any adverse event that may endanger the subject and may require intervention to prevent more serious conditions is considered a serious adverse

event. The determination of major medical events should be based on the "WHO Adverse Event Terminology – Main List of Terms". These terms refer to serious disease states or descriptions of serious disease states.

These events are reported as serious adverse events (SAEs) because they may be associated with serious disease conditions and, compared to other reporting methods, reporting them as SAEs ensures heightened attention and facilitates necessary actions.

6.3.3 Unintended Adverse Events

An unexpected adverse event refers to any adverse drug reaction (ADR) whose characteristics or severity differ from those described in the package insert of the marketed product. Supplementary information regarding the characteristics or severity of known or documented adverse events also constitutes part of the unexpected adverse event report. For instance, events that are more specific or severe than those described in the package insert should be classified as "unexpected." Specific examples include: (a) acute renal failure, which has been previously reported as an adverse event, subsequently complicated by interstitial nephritis; and (b) hepatitis initially reported as acute liver necrosis.

6.3.4 Relationship Between Adverse Events and Study Drug

The evaluation of the relationship between a adverse event and the investigational drug is a comprehensive clinical judgment made based on all available information when completing the case report form.

"Not relevant" may include:

1. There are clear alternative explanations, such as traumatic bleeding at the surgical site;
perhaps
2. Unreasonable, such as when a subject is hit by a car, but there is no indication that the event was caused by the drug-induced disorientation; or cancer developing just days after the start of the drug.

A 'yes' evaluation indicates that there are reasonable grounds to suggest a potential association between the adverse event and the study medication.

The following factors should be considered when assessing the relationship between adverse events and the investigational drug:

- Short-term occurrence after drug administration: This adverse event should occur after administration. The duration between medication and the occurrence of the event should be considered during clinical evaluation.

- The event disappeared after discontinuation of administration (cessation of stimulation) and reappeared after resumption of administration (repeated stimulation): When analyzing the clinical course of a suspected event, the response after discontinuation of administration (cessation of stimulation) or after resumption of administration (repeated stimulation) should be fully considered.
- Underlying, comorbid and comorbid conditions: Assess the natural course of the disease, the treatment process and all other conditions the patient may have in each report;
- Concomitant medications or treatments: The other medications taken by the subject or other treatments received by the subject should be examined to determine whether any of them may have caused the adverse event.
- Known response patterns of a specific class of drugs: clinical/preclinical
- Pharmacology and Pharmacokinetics of the Investigational Drug: The pharmacokinetic characteristics (absorption, distribution, metabolism, and excretion) of the investigational drug should be considered in conjunction with the individual pharmacodynamic response of each subject.

6.3.5 Recording of Adverse Events

All adverse events occurring after the subject signs the informed consent form must be fully documented in the subject's case report form.

Records must be supported by original documentation. Laboratory test abnormalities deemed clinically relevant (e.g., those leading to early study withdrawal, requiring treatment, or causing significant clinical manifestations, or those considered clinically relevant by investigators) should be reported as adverse events. Each event must be described in detail, including the start and end dates, severity, relationship to the investigational product, measures taken, and the outcome of the event.

6.4 Reporting of Serious Adverse Events

From the time of informed consent signing until 30 days after the completion of the last dose, any defined serious adverse event (SAE), including laboratory test abnormalities meeting the SAE definition, must be immediately reported to the designated personnel in the study documents (within 24 hours of the investigator's knowledge). The SAE report form must also be completed and submitted to the designated personnel in the study documents within 24 hours of the investigator's knowledge.

Each serious adverse event should be followed up until resolution or stabilization,

with an updated report submitted to the designated personnel. A simple Level 4 laboratory test abnormality (according to the CTCAE 5.0 criteria) should not be reported as a serious adverse event unless the investigator determines that the abnormality meets the International Conference on Harmonisation (ICH) criteria for serious adverse events (as defined in Section 6.3.2). A Level 4 laboratory test abnormality that occurs at baseline and is a manifestation of the disease according to the CTCAE 5.0 criteria should not be reported as a serious adverse event, particularly if the abnormality is present but the patient is still allowed to enroll or is not excluded from enrollment. If there is any doubt about whether the abnormality should be reported as a serious adverse event, the investigator may consult the study monitor. A Level 4 laboratory test abnormality should be recorded on the "Laboratory Data" page and regularly cross-checked by the medical monitor.

According to the requirements of local laws and regulations, serious adverse events must be reported to the ethics committee and the drug regulatory authority.

7. Appendix

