3.5 Subject Withdrawal from the Study

Discontinued cases refer to patients who cease medication for various reasons during clinical studies. Patients meeting the following criteria will be withdrawn from the study:

- The patient or their legal representative requests withdrawal;
- According to the investigators 'opinion, continued participation in the study would be harmful to the patient's health.
- patients with severe non-adherence or serious protocol violations;
- The patient is pregnant, and pregnancy should be reported as a serious adverse event.
- When other diseases occur concurrently during the study, and based on the investigator's assessment that the disease will significantly affect the evaluation of the patient's clinical condition, and when discontinuation of the current treatment regimen is required;
- other malignancies requiring treatment;
- lost to follow-up;

- Use of prohibited drugs or other drugs that the investigator judges may cause toxic reactions or bias the results of the study;
- The patient died.

All patients who withdraw from the study should have the reason for withdrawal recorded in the case report form and the patient's medical record.

All patients who withdrew due to adverse events or abnormal laboratory findings should be followed up until the adverse event resolved or stabilized, with subsequent outcomes recorded. If a patient died during the trial or within 30 days after trial completion, the investigator must be notified by the researchers. The cause of death must be documented in detail on the Serious Adverse Event (SAE) report form within 24 hours.

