3.7.3.1 Research Visits

- Screening visit should be conducted within 28 days prior to initiation of study drug therapy.
- The treatment period refers to the duration from the initiation of the first study drug administration until the patient discontinues the study drug therapy.
- Patients were evaluated every 8 weeks after discontinuation of study drug therapy due to non-progressive conditions. If disease progression was confirmed, they would enter the follow-up period. During this period, contact with patients should be maintained every 3 months until the patient's death was recorded, to collect data on overall survival.

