3.8.3 Post-treatment

After treatment (non-progression end of treatment), examinations should be performed every 3 months until disease progression (see flowchart).

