3.8.5 Follow-up after disease progression

Contact patients every 3 months (via in-person visits or telephone calls) to obtain data on overall survival and post-study chemotherapy. Follow-up should be conducted every 3 months until the patient's death. During each follow-up visit, the following information should be collected:

- Patient survival status.
- Disease status and progress date (if applicable).
- Date of death (if applicable).
- Record all new anticancer therapies.

Note: Patients with tumor progression should be treated as other patients with advanced colorectal cancer.

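### SAEs are reportable until 30 days after the last dose, but no contact is scheduled to close that window, and deaths are reported under a second window with a different starting point

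*Protocol*

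**What the plan says.** **SAE window.** Section 6.4 requires SAEs to be reported "From the time of informed consent signing until 30 days after the completion of the last dose". The duty starts when the site learns of the event: the report is due "within 24 hours of the investigator's knowledge".

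**AE recording.** Section 6.3.5 gives a start and no end: "All adverse events occurring after the subject signs the informed consent form must be fully documented in the subject's case report form".

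**Visits after treatment.** The flowchart in 7.5 shows one post-treatment visit, due within seven days, with vital signs, ECG and laboratory tests. It does not say seven days after what. Section 3.7.3.1 defines the treatment period as running "until the patient discontinues the study drug therapy", which makes drug discontinuation the natural anchor.

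**Next contact, stopped without progression.** Section 3.7.3.1 and the flowchart give 8 weeks: "Patients were evaluated every 8 weeks after discontinuation of study drug therapy due to non-progressive conditions". Section 3.8.3 gives 3 months: "After treatment (non-progression end of treatment), examinations should be performed every 3 months until disease progression".

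**Next contact after progression.** Section 3.8.5: "Contact patients every 3 months (via in-person visits or telephone calls) to obtain data on overall survival and post-study chemotherapy". The items listed there are survival status, disease status and progression date, date of death, and new anticancer therapy.

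**Deaths.** Section 3.5 requires the cause of death on the SAE form within 24 hours in this case: "If a patient died during the trial or within 30 days after trial completion". Trial completion is not defined.

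**The concern.** A reporting window is only as good as the contacts that feed it. Section 6.4 is triggered by the investigator's knowledge, so an SAE in the later part of the 30 days enters the data only if something brings it to the site. The schedule gives every patient an early visit and then nothing until well after the window has shut. The one follow-up contact whose content is itemised does not ask about adverse events.

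Deaths raise a second problem. Sections 3.5 and 6.4 both use 30 days but count from different points. Patients are followed for survival long after the last dose, so the two starting points can be far apart, and two sites or two data managers could classify the same death differently.

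Safety is a stated objective and a secondary endpoint (sections 2 and 3.7). With 37 patients planned, each patient with a missed SAE lowers the reported proportion by 1/37 = 2.7 percentage points.

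**Working it through.** The protocol gives no figure to reproduce here. The check is calendar arithmetic.

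**Inputs.** Window of 30 days from the last dose (6.4). Visit no later than 7 days after an unstated anchor (7.5). Anlotinib on days 1 to 14 of a 21-day cycle and sintilimab once every 3 weeks (3.6.1), with sintilimab taken here as given on day 1. Next contact at 8 weeks (3.7.3.1, 7.5) or 3 months (3.8.3, 3.8.5).

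**Uncovered days** = 30 − (latest day of the visit, counted from the last dose).

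| Seven days run from | Last dose given | Latest visit, days after last dose | Uncovered |
|---|---|---|---|
| Last dose | either drug | 7 | 30 − 7 = 23 (77%) |
| End of cycle, day 21 | anlotinib, day 14 | (21 − 14) + 7 = 14 | 30 − 14 = 16 (53%) |
| Stop decision on day 22 | anlotinib, day 14 | (22 − 14) + 7 = 15 | 30 − 15 = 15 (50%) |
| End of cycle, day 21 | sintilimab, day 1, no later anlotinib | (21 − 1) + 7 = 27 | 30 − 27 = 3 (10%) |

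A day-22 decision in the last row would give 2 days instead of 3. Seven days is an upper limit for the visit, so an earlier visit leaves more of the window uncovered.

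**Next scheduled contact**, counted from the last dose:

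- 8 weeks: day 56, which is 56 − 30 = 26 days after the window closes.
- 3 months: about day 91, which is 91 − 30 = 61 days after it closes.
- Counted from a day-7 visit instead: day 63 or about day 98.

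In none of these readings is a contact placed at or shortly after day 30. One exception is possible. Section 3.6.2 allows dosing to be suspended. If the formal stop came 23 or more days after the last dose, a visit seven days later would fall on day 30 or beyond (23 + 7 = 30). That would close the window by chance and only for those patients.

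**Deaths, side by side.** Take a cancer death six months after the last dose, in a patient still in survival follow-up.

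- Under 6.4, day 30 has passed, so the death is outside the window.
- Under 3.5, if survival follow-up counts as part of the trial, the death needs an SAE form within 24 hours. Section 3.7.3.1 describes this follow-up under research visits, so that reading is open to a site.
- Section 6.3.1 does not settle the matter. It makes progression that meets a serious criterion an SAE but sets no window.
- The length of follow-up is itself inconsistent. Sections 3.7.3.1 and 3.8.5 continue to death, while flowchart footnote 9 stops at 1 year after progression or death.

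**The case against.** The strongest reply is that 6.4 creates a duty to report what the investigator learns and does not promise active enquiry at day 30. A reporting window can outlast the last visit without the protocol contradicting itself. That stands: this is a weakness in ascertainment, not an internal contradiction.

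Other routes also exist. Section 3.8.4 provides unscheduled visits, with adverse events recorded. Section 3.5 follows patients withdrawn for adverse events or laboratory abnormalities until resolution or stabilisation. The post-progression contact collects the date of death, so a fatal event would be learned of, though late. These routes are driven by need or cover a subset, and none asks every patient about the full 30 days. The gap is therefore in scheduled contact, not in all contact.

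The adverse-event row of the flowchart is incomplete in the available text and may extend into the follow-up columns. A line across columns would still not add a contact between the seven-day visit and week 8.

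Three stronger readings are tempting but not supported:

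- **That most of the window is always unobserved.** This holds only if the seven days run from the last dose, and the flowchart does not state the anchor.
- **That 3.5 makes every death in survival follow-up a fatal SAE.** Trial completion is undefined, and the sentence sits in a section about patients who stop medication, so a patient-level reading is possible. The medians of 8.6 months (PFS) and 22.9 months (OS) in the introduction do not size the problem, because they come from an earlier trial population that included liver metastases and ECOG 2.
- **That late SAEs would undermine the 13.3% rate in the introduction.** That figure is for treatment-related events of grade 3 or higher, which is a different measure.

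**Conclusion.** The point holds as a gap in scheduled ascertainment plus an inconsistency in the rule for deaths. The uncovered part of the SAE window is 23 of 30 days if the visit is counted from the last dose, 15 to 16 if it follows the end of a cycle finished with anlotinib, and about 3 if the last dose was sintilimab on day 1. Which applies depends on an anchor that the protocol should state. That no contact is planned to close the window does not depend on it.

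Some late SAEs may be missed. The number cannot be estimated, because the protocol gives no rate of late events; 2.7 points per missed patient is only a unit of scale. The two death windows can give different fatal-SAE counts if survival follow-up is taken as part of the trial. The trial is not invalidated, but its safety window is not supported as written, and the repair is cheap.

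**What to change.** 1. Add to 3.7.3.1 and the flowchart one telephone or visit contact for every patient at about day 30 after the last dose, recording AEs and SAEs. Section 3.8.5 already accepts telephone contact.
2. State in the flowchart the event from which the seven-day post-treatment visit is counted.
3. Reconcile 3.5 with 6.4 so that one rule governs the reporting of deaths, and define trial completion if the term is kept. The protocol gives no basis for preferring either window, so the choice belongs to the sponsor.
4. Tabulate SAEs that are disease progression separately from other SAEs, so that cancer deaths can be told apart whichever rule is adopted.
5. While editing these sections, reconcile the 8-week and 3-month intervals after stopping without progression, and the two end points for follow-up after progression.

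Cost: about 37 calls, one per patient, and wording changes. The reported SAE rate may rise slightly because ascertainment is more complete.

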7.1 General Status (ECOG Score)

classify	description
0	Full capacity to perform all pre-disease behaviors without restriction. (Karnofsky 90-100 points)
1	Significant limitation of physical activity, but able to walk and perform light physical or sedentary work (e.g., housework and office work). (Karnofsky score 70-80)
2	Capable of walking and performing basic self-care activities, but unable to complete any work-related activities. The time spent on ambulation and alertness exceeds 50% of the total. (Karnofsky score 50-60)
3	Only limited self-care is possible. More than 50% of the waking time requires bed rest or sitting. (Karnofsky score 30-40)
4	Complete disability with loss of mobility. No ability for self-care. Completely bedridden or sedentary. (Karnofsky score 10-20)

